6. CONSENT PROCESS

Upon identification of a subject meeting all inclusion and no exclusion criteria, subjects will be approached by study research personnel (either the PI or a Research Assistant) to obtain informed consent prior to initiation of any study activities. This will occur while patients are in the ED and under the primary care of the ED physician. Given the goal of randomization within one-hour of presentation to the ED, care will be taken to not interfere with ongoing medical care while still ensuring timely approach for enrollment. Consent forms describing in

appropriate detail the study interventions, study procedures, and risks will be given to the participant and/or their LAR. Consent forms will be Institutional Review Board (IRB)-approved and the subject/LAR will be asked to read and review the document. A verbal explanation will also be provided in terms suited to the subject's comprehension of the purposes, procedures, and potential risks of the study and of their rights as research participants. Participants will have the opportunity to carefully review the written consent form and ask questions prior to signing. The participants will have the opportunity to discuss the study with their family or surrogates and think about it prior to agreeing to participate. The participant/LAR will sign the informed consent document prior to any study procedures being done. Subjects/LARs will be informed that participation is voluntary and that they may withdraw from the study at any time, without prejudice. A copy of the informed consent document will be given to the participants for their records. The informed consent process will be conducted and documented in the source document (including the date), and the form signed, before the participant undergoes any study-specific procedures. A witness signature will be not be included on the consent form. However, a signature of the study personnel completing the consent is included and required. The rights and welfare of the participants will be protected by emphasizing to them that the quality of their medical care will not be adversely affected if they decline to participate in this study.

When the patient's capacity for informed consent is questioned due to the nature of the stroke itself or other mental impairment, capacity will be determined using the UABCC Form. This method of determining capacity consists of a 10-item questionnaire that can be delivered in 5-10 minutes and has been found to have high sensitivity and specificity and good interrater reliability⁵³. If a subject is determined to not have capacity for consent, the LAR will be identified and approached for consent. If and when the study subject regains capacity, they will be approached for continued participation. If the subject/LAR consents for participation he/she will sign the informed consent document prior to any procedures being done specifically for this study.

After a patient consents for participation in the study, he/she will be randomized to either hyperoxia or medical air treatment. Randomization will occur in blocks of 20 using excel and subject treatment assignments will be determined prior to initiation of the study and enrollment of subjects.

In addition to the traditional paper consent process, the ongoing COVID-19 pandemic has necessitated the use of an optional electronic consent (eConsent) process. Bringing a paper consent form and pen to the bedside of a patient with known or suspected COVID-19 and then taking these out of the room would violate infection control principles and policies. Additionally, the current pandemic presents challenges to obtaining consent from the LAR who may not be physically present in the ED at the time of consent due to a variety of reasons including limited visitation policies and/or the need to self-quarantine. Therefore, an eConsent process will also be used. In these cases, if a subject has decisional capacity and/or the LAR is physically present in the ED, but there is concern for COVID-19 infection, the research team will call the subject on their hospital room phone or personal phone and request to email the subject/LAR a copy of the eConsent form. The same process for informed consent, including explanation of the consent process and study, and opportunity for questions, will occur via telephone. At the end of the conversation, the subject/LAR will be asked to complete the eConsent Survey via REDCap. The research team and witness signatures will also be documented via REDCap. The same process will be used if the subject lacks decisional capacity and the LAR is not physically present in the ED for consent.

As blood will be collected as part of the study protocol for analysis of serum biomarkers of stroke, subjects will also be consented to have any remaining serum maintained in CU repository in the Emergency Medicine Research Lab. Blood sample collection for research purposes will not be optional for subjects participating in the study, as reflected in the consent form. However, use of the blood sample for future research is optional. Blood samples will be obtained from consenting subjects and immediately processed for storage in freezers with unique sample identifiers. Subjects will not have access to any individual results from this study or such future analysis. Future analysis of blood samples markers will be subject to COMIRB requirements, and approval for the initiation and continuance of such activities. Upon completion of this study, blood values and correlating clinical information will be linked and all information will be de-identified. All blood analyses will be completed in aggregates, not at the individual subject level.

7. STUDY PROCEDURES

As part of the screening and enrollment process, patients with suspected AIS will have either a non-contrast CT head with RAPID calculation of ASPECT score or a CT-perfusion head. Using standard stroke alert treatment protocols at this institution, the RAPID software is used in most potential stroke patients at our institution and will be used to calculate infarct and penumbral volume and targeted diffusion/perfusion mismatch for this study. As part of the screening process, medical charts and EMS reports will be accessed by study personnel as needed to ensure potential subjects meet all inclusion/exclusion criteria. The screening and enrollment procedures along with collection of initial vitals will occur almost simultaneously given the very acute nature of the presentation and desired short interval from ED presentation to randomization. No data will be collected during the screening process that is not part of routine patient care prior to subject enrollment. Routine patient demographics, past medical history, medications, and prehospital assessments will be obtained from chart review. No research data that is not already part of routine patient care will be entered into the subject medical records. Randomization will occur in a 1:1 fashion between the two treatment groups. The estimated study duration is 30 months to allow for full enrollment of subjects and the 3-month mRS assessment. Each subject will be followed for a total of 90 days from enrollment to final assessment. No results from this study will be shared with subjects.

[figure not shown]
Once consented and enrolled in the study, subjects will have the following procedures: (See Table 1 for Schedule of Activities).

1. *Infarct progression:*

- a. Initial CT-perfusion head or non-contrast CT-Head with RAPID ASPECT score – multimodal CT-head imaging will be obtained upon ED presentation according to local stroke protocols. Targeted mismatch criteria will be based on previous standards identified in the DEFUSE 3 trial, using RAPID generated CT maps (RAPID, iSchema View, Menlo Park, CA)⁵⁷. This study measurement will be completed as part of the screening process to ensure eligibility with regards to a target mismatch lesion. However, upon completion of the CT-perfusion or non-contrast CT-Head, the total volume of at-risk tissue (both penumbral and infarcted tissue) will also be determined and recorded. This is part of the routine medical treatment for acute stroke patients.
- b. Follow-up MRI-head, or a repeat CT-head in patients unable to obtain an MRI, will be obtained at roughly T3 according to standard stroke imaging protocols. The total volume of infarcted tissue will be determined and recorded. Repeat

imaging usually between 24-72 hours is part of the standard of care for most stroke patients to ensure there has not been hemorrhagic conversion. Only these repeat imaging studies that were routinely obtained for standard patient care will be used for further determination of infarct progression. Specific study-dedicated imaging will not be obtained.

- c. The ratio of the volume of at-risk tissue (T0 – penumbral and infarcted tissue) to the volume of final infarct at subsequent reimaging will be compared between the placebo and hyperoxia groups. Volume assessments will be generated from both the CT-perfusion or non-contrast CT-Head at screening and the subsequent MRI using RAPID (iSchema View). These image files contain PHI, but are de-identified prior to processing by RAPID under the below process and PHI remains within the UCHealth firewall.

2. Analysis of serum markers of free radical ischemic-reperfusion injury and hyperoxic lung injury:

- a. Whole blood and serum samples will be collected using routine phlebotomy and venipuncture procedures. Serum will be collected in standard blood collection tubes, subsequently isolated from whole blood and stored in small aliquots for further analysis. All samples will be labeled with unique study identifiers to ensure blinded analysis but still allowing for correlation with specific patient outcomes. To decrease variability between analysis of serum markers, serum will be collected and stored in the ED cold storage facility until samples can be run in batches.
- b. Analysis of specific markers (MMP-9, IL-6 and IL-8): Serum levels will be determined using the Millipore custom-designed Milliplex® multiplex assays in accordance with the manufacturer recommended protocol. This assay uses bead-based immunodetection of multiple biomarkers simultaneously from 25uL of serum in 96-well plates. The technology also contains internal controls to help ensure accurate determination of serum levels of biomarkers. All sample analysis will be performed on a blinded basis in batches, using a single Luminex xMap

core instrument. Further undetermined biomarkers may also be analyzed separately and/or in conjunction with these selected biomarkers. This technology has the ability to analyze related biological pathways that may be related to underlying pathophysiology that is being assessed through the analysis of MMP-9, IL-6 and IL-8.

3. *Functional Outcomes:*

- a. NIHSS score: The NIH Stroke Scale (NIHSS) is a standardized tool to measure stroke severity. Study observers will be required to complete the National Stroke Association NIHSS certification online course. As part of the training, interrater reliability between study observers will be determined. This assessment is part of all initial stroke evaluations by ED and/or neurology physicians. Subsequent NIHSS assessments at T₁ and T₂ will be video-recorded by trained study personnel and/or EDRA. However, in the case the videotaping is not permitted by a performance site, NIHSS-trained personnel (RN, MD, or PA) who are caring for the patient, will be asked to complete and score the NIHSS. In the event that the clinical team is unable to complete this assessment, the research team, also NIHSS-trained, will complete this assessment. In all cases, who/how the NIHSS was completed will be documented and blinding to the study intervention will be attempted when possible. The preference will be to have the score determined in a blinded manner upon review of the assessments at a subsequent time point.
- b. mRS scoring: The modified Rankin Scale, mRS, is another functional scale that assesses for neurologic disability on a scale of 0-6 (0-asymptomatic; 6-death). A historical mRS will be extracted from the patient chart and/or calculated at patient presentation. Patients and/or their caregivers will be interviewed by phone at 3months using a series of standardized questions regarding their neurologic disability to determine this score.

4. *Arterial puncture and ABG* – Hyperoxia (PaO₂ >200mmHg) will be confirmed by an ABG sample from subjects. These will be obtained by licensed medical personnel trained to perform arterial punctures (i.e. nurses, physicians, respiratory therapists). Standard procedures for obtaining an arterial blood sample will be employed to reduce the risk of complications. To decrease variability between ABG analysis, ABGs will be performed using standard operating procedures. The site of the arterial puncture and correlating extremity will be evaluated for potential complications (increased pain, discoloration, erythema, hematoma formation, bleeding). If there are any concerning findings on these exams, the study PI will be notified and the subject will be monitored again at T₂ and/or until the event is felt to resolve.

5. *Vital signs* - The determination of need for additional supplemental oxygen in a patient that becomes hypoxic (pulse oximetry<94%) will be determined by the subject's treating physician irrespective of study interventions. Should a patient be found to require additional supplemental oxygen while enrolled in the study, this will be noted and the patient will continue through the final study assessments. The patient's treating physician will also be responsible for routine monitoring and interpretation of other vital signs such as blood pressure and heart rate. If at study assessment time points the study personnel note a subject to have significant vital sign abnormalities (SpO₂<94%, SBP>180mmHg, DBP>110mmHg, SBP<90mmHg, HR>120, HR<50), the study PI and patient's treating physician will be notified to ensure proper documentation. Interventions will be left to the discretion of the patient's treating physician.

Table 1: Schedule of Activities:

Procedures	Baseline/Enrollment ED presentation -T0 (ED arrival +/-60min)	T1 (T0+4hours +/- 20min)	T2 (T0+24hours +/- 4hours)	T3 - Final Assessment (T0+3mo +/- 2weeks)
Informed consent	X			
Demographics	X			
Medical history	X			
Randomization	X			
Administer study intervention		X		
Vital signs: HR, BP, RR, SpO ₂	X	X	X	
ABG		X		
CT-perfusion or CT-head with ASPECTS	X			
Repeat MRI-head (CT-head if unable to get MRI) ^a			X	
Serum sample ^b	X	X	X	
NIHSS	X	X	X	
mRS	X			X
Adverse event review and evaluation		X	X	

^a only routine re-imaging will be obtained
^b tested for selected biomarkers (IL-6, IL-8, and MMP-9)

Assessment of study intervention adherence:

1. Compliance with study interventions will be directly observed at the given time points. If at any observation period a subject is found not to be compliant with the study intervention, medical records will be reviewed to determine the timing of termination of the supplemental oxygen/medical air.
2. All cases of non-compliance with study interventions will be recorded.

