4.1. SUBJECT POPULATION

Eligible subjects will include acute ischemic stroke (AIS) patients aged 18 years or older who present to the UCH ED. There will be no specific selection of subjects based on sex, race or ethnicity, age, or socioeconomic status. We anticipate the study population to be representative of that of the greater Colorado Springs and Aurora, CO area with the exception that stroke prevalence increases with age and this will likely be reflected in the final study population.

Subjects with a suspected stroke who are normoxic at baseline (room air SpO₂≥94%) and have either 1) a target mismatch lesion on CT-perfusion [defined by RAPID automated software demonstrating a ratio of PWI_{Tmax>6} lesion volume/Infarct volume (with cerebral blood flow <30% normal) greater than 1.2 or 2) a non-contrast CT-head RAPID ASPECT score of 10 (suggesting a patient has not completed their infarct), a NIHSS≥ 1, and a LKW ≤ 12 hours will be screened for eligibility. While some vulnerable populations (i.e. children and prisoners) will be excluded, AIS by the nature of the disease has the potential to impair a subject's capability to give informed consent and places them in the category of a vulnerable population. All subjects will be evaluated for the ability to give informed consent through use of the University of California, San Diego, Brief Assessment of Capacity to Consent (UABCC) Form⁵³. In cases where the subject is determined to lack the ability to provide consent, the subject's legally authorized representative (LAR) will be approached. Consent forms describing in appropriate detail the study interventions, study procedures, and risks will

be given to the participant and/or their LAR. If and when the study subject regains capacity, they will be approached for continued participation. If the subject/LAR consents for participation he/she will sign the informed consent form prior to any study procedures being done.

In terms of potential pregnant women, it is anticipated that most women will be older than likely childbearing age. While supplemental oxygen use in pregnant women experiencing fetal distress is routine, the effects of maternal hyperoxia on a developing fetus are unknown. Those of likely childbearing potential will be excluded. If a subject withdraws for any reason from the study, he/she will be replaced to meet the enrollment goal when possible. Our target enrollment will be 200 patients (~100 per arm).

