4.2. INCLUSION / EXCLUSION CRITERIA

Inclusion Criteria: In order to be eligible to participate in this study, an individual must meet all of the following criteria:

1. Provision of signed and dated informed consent form from patient or legal authorized representative (LAR)
2. Subject or LAR stated willingness to comply with all study procedures and availability for the duration of the study
3. Males and female (of unlikely childbearing capacity) aged over 18 years
4. Exhibiting signs and physical examination findings suggestive of an acute ischemic infarction (with either):
 - a. A target mismatch profile of CT-perfusion or MRI determined by RAPID automated software to have a ratio of PWI_{T_{max}>6} lesion volume/DWI lesion volume >1.2 and NIHSS $\geq 1^{54}$
 - b. A RAPID automated software calculated non-contrast CT-head ASPECT score of 10 and LKW ≤ 12 hours (in patients with symptoms discovered upon waking, the LKW is defined at the midpoint between going to sleep and awakening based on previous studies that suggest most strokes during sleep occur close to awakening)⁵⁵
5. Normoxic; a pulse oximetry of 94% or greater at time of screening without the use of supplemental oxygen

Exclusion Criteria: An individual who meets any of the following criteria will be excluded from participation in this study:

1. Current use of supplemental oxygen
2. Prisoner
3. Pregnancy or those of likely childbearing potential (i.e. age <50, no documented negative pregnancy in last 24 hours, no documented history of hysterectomy)
4. Documented blood glucose <70mg/dL
5. Concurrent treatment with another investigational drug or other intervention
6. Documented history of any of the following chronic respiratory illness that require pulmonary vasodilators or supplemental oxygen at baseline: Chronic Obstructive Pulmonary Disorder (COPD), Emphysema, Interstitial Lung Disease, Restrictive Lung Disease, Pulmonary Hypertension, Pulmonary Fibrosis
7. Documented history of any of the following autoimmune diseases: systemic lupus erythematosus, rheumatoid arthritis, scleroderma, primary biliary cholangitis, multiple sclerosis, inflammatory bowel disease

8. Currently being treated for an acute myocardial infarction and/or decompensated heart failure at the onset of initial ED presentation as reported by the ED provider
9. Plans for treatment with either IV tPA (alteplase) or endovascular therapy

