17. DATA ANALYSIS PLAN

The primary endpoint of this study is feasibility. We hypothesize that the challenges of enrolling and randomizing AIS patients to a therapeutic intervention within less than one hour of ED presentation can be addressed. The number of potential subjects meeting the inclusion criteria and the relative rates of enrollment over time will be tracked. Additionally, the timing to enrollment and initiation of treatment intervention will be monitored. The primary endpoint of this study is feasibility as measured by the mean time from presentation to the ED to randomization and initiation of intervention. We hypothesize that we will be able to enroll, randomize and initiate treatment intervention in less than one hour for 80% of the enrolled subjects.

This study is not powered to detect significant differences in secondary or exploratory outcomes. However, analysis of secondary outcomes will occur both on an intention-to-treat and a per-protocol basis. Penumbral salvage will be reported as an average and as a standard deviation of the mean. We plan to enroll a total of 200 patients. Based on previous data that showed a decrease in the relative infarct volume growth (infarct volume at presentation/infarct volume at 4 hours) in patients treated with hyperoxia (87.8 +/-22%) compared to controls (149.1 +/- 41%)²⁹, 5 patients per arm would be needed to detect a similar difference with a power of 90% and type I error rate (α) of 0.05⁶². However, this effect was seen in a small study with less than 10 patients per treatment arm. Thus, such dramatic changes in infarct volume may not be expected, but even a smaller reduction in infarct volume will be clinically important as small reductions in infarct volume can have profound clinical effects if it is in a key cerebral territory. If you assume 20% of patients for some reason do not receive standard follow-up imaging to allow for calculation of infarct progression, a standard deviation of 41%, 80% power and α of 0.05, the proposed sample size will be able to detect an absolute difference in infarct volume growth of 18% between the control and hyperoxia.

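### Criterion 4b subjects without baseline perfusion imaging have no at-risk volume as the protocol defines it, yet the plan takes that volume from their non-contrast CT and counts them in the 18% detectable difference

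*Combined protocol and SAP*

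**What the plan says.** Section 4.2 offers two imaging routes into the trial. Criterion 4a needs a RAPID mismatch on CT-perfusion or MRI. Criterion 4b needs "A RAPID automated software calculated non-contrast CT-head ASPECT score of 10 and LKW" within 12 hours, with no perfusion scan. Section 7 and Table 1 likewise treat the two screening scans as alternatives.

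The volumes behind the mismatch are a Tmax>6 lesion set against either an infarct core with cerebral blood flow below 30% of normal (section 4.1) or a DWI lesion (section 4.2, criterion 4a). ASPECTS appears only as a score. Section 4 groups it with CT-perfusion as quantitative or semi-quantitative measures, and section 4.1 reads a 10 as a sign that the infarct is not complete.

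On the imaging outcome, section 7, item 1(a), says that "upon completion of the CT-perfusion or non-contrast CT-Head, the total volume of at-risk tissue (both penumbral and infarcted tissue) will also be determined". Item 1(c) compares between arms the ratio of that baseline volume to final infarct volume, and adds: "Volume assessments will be generated from both the CT-perfusion or non-contrast CT-Head at screening and the subsequent MRI using RAPID".

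Section 17 says "We plan to enroll a total of 200 patients". It then allows for one kind of loss, "If you assume 20% of patients for some reason do not receive standard follow-up imaging to allow for calculation of infarct progression", and with "a standard deviation of 41%, 80% power and α of 0.05" reports a detectable absolute difference in infarct growth of 18%.

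**The concern.** Items 1(a) and 1(c) describe a measurement that the protocol's own definitions do not allow for some admitted subjects. A non-contrast CT yields neither a Tmax>6 volume nor a blood-flow core, and no other method is offered. Nothing limits the volume analyses to subjects with perfusion imaging, takes account of entry route, or says what happens when the baseline volume is missing.

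Penumbral salvage is the first-listed secondary outcome in section 4 and is meant to inform a later trial. Section 17 promises intention-to-treat and per-protocol analyses of secondary outcomes. An analyst following the text would have to drop the affected subjects without a stated rule or give them an invented baseline, and might make that choice with outcome data in hand. The 18% would also be quoted for more subjects than can contribute.

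**Working it through.** **Can the volume be obtained?**

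| Quantity | What it needs | 4b subject with non-contrast CT only |
|---|---|---|
| Baseline at-risk volume, item 1(c) | Penumbra plus core | Not available by the protocol's definitions |
| Relative infarct growth, section 17 | Infarct volume at presentation | Not measured; if set to zero because ASPECTS is 10, a change relative to it is undefined |
| Final infarct volume, item 1(b) | Routine re-imaging | Available if re-imaged |

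**Inputs for the 18%.** Section 17 gives 200 subjects, 20% without follow-up imaging, SD 41 percentage points, 80% power and alpha 0.05. Section 7 gives the allocation: "Randomization will occur in a 1:1 fashion between the two treatment groups". Sidedness is not stated. Two-sided is assumed because it reproduces the plan's figure; one-sided gives 16.1 points.

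**Reproducing the plan.** Evaluable subjects per arm: 100 × (1 − 0.20) = 80.

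Normal approximation: detectable difference = SD × √(2/n) × (1.960 + 0.842) = 41 × √(2/80) × 2.802 = 6.483 × 2.802 = 18.2 points. The two-sample t-test (noncentral t, 2n − 2 degrees of freedom) gives 18.3. Both agree with the stated 18%, so the arithmetic is sound on its inputs. It uses all 100 per arm before the follow-up loss, which means that every subject is taken to have a usable baseline volume.

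**Allowing for missing baseline volumes.** Let p be the share of subjects with baseline perfusion imaging, equal in the two arms and unrelated to follow-up loss. Then n per arm = 80 × p. The documents do not give p, so the rows below 100% are assumptions. Results are from the t-test.

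| p | n per arm | Detectable difference at 80% power | Power for 18 points |
|---|---|---|---|
| 100% | 80 | 18.3 | 79% |
| 90% | 72 | 19.3 | 74% |
| 75% | 60 | 21.1 | 66% |
| 50% | 40 | 26.0 | 49% |
| 25% | 20 | 37.3 | 27% |

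The normal approximation gives 19.1, 21.0, 25.7 and 36.3 points for the last four rows, within about one point.

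**The case against.** Four points can be made for the plan.

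- **Perfusion imaging may be common.** Section 7, item 1(a), refers to multimodal CT under local stroke protocols, and section 7 says RAPID is used in most potential stroke patients. A 4b subject may therefore also have a CT-perfusion, for example one with a mismatch ratio of 1.2 or less. This stands. A reader might infer that the whole 4b route lacks baseline volumes, but the documents do not show that. Only 4b subjects without perfusion imaging are affected. The gap remains because nothing requires the scan and the two modalities are consistently given as alternatives.
- **The outcome is secondary.** Section 17 says the study is not powered for secondary or exploratory outcomes, and the primary endpoint is feasibility. This stands and limits the severity. It does not make the volume computable, and section 17 still publishes the 18%.
- **The loss may be small.** With 90% coverage the detectable difference rises by about one point. This stands. Nothing in the documents favours any row of the table over another.
- **The zero-baseline argument can be pushed too far.** A reader might take ASPECTS 10 to mean an infarct volume of zero. Section 4.1 says only that it suggests an uncompleted infarct. The growth ratio in section 17 is also described as the measure of the cited pilot study, while item 1(c) specifies a different ratio for this trial. So the firm finding is that the baseline is unmeasured; the zero baseline follows only if someone imputes it. Conversely, criterion 4a sets no minimum core, so a zero or near-zero core can occur even with perfusion imaging.

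**Conclusion.** The point holds for criterion 4b subjects who have no baseline perfusion imaging. For them the rule in items 1(a) and 1(c) cannot be carried out under the protocol's definitions of penumbra and core, and the 18% in section 17 is correct only if there are no such subjects. The cost lies between about one point (19.3 at 90% coverage) and a doubling of the detectable difference (37.3 at 25%). Where it falls cannot be determined from the documents. These figures assume a two-sided test, SD 41 points, 20% follow-up loss and equal coverage in the two arms.

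A reader might go further and conclude that the trial is too small or that section 17 is miscalculated. Neither is supported: the calculation reproduces, the outcome is secondary, and the feasibility endpoint and the sample size of 200 do not depend on it. This should be fixed but is not critical.

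**What to change.** **Section 7, items 1(a) and 1(c).** Delete non-contrast CT as a source of at-risk, penumbral or baseline infarct volume. Limit penumbral salvage and infarct growth to subjects with a baseline perfusion volume, by CT or MRI. Because perfusion imaging does not rule out a zero or near-zero core, use the at-risk-volume measure of item 1(c) or absolute growth, not growth relative to core. As item 1(c) is worded the final infarct is the divisor, so state how a final volume of zero is handled.

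**Section 17.** State that 18% assumes a baseline volume in every subject, and give the detectable difference for the share expected to have perfusion imaging, or across the range tabulated above. Describe the imaging set as a defined subset of those randomised, so that the intention-to-treat wording is not read as covering everyone for this outcome.

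**Optional.** Report the final infarct volume already recorded under item 1(b) for all re-imaged subjects, adjusted for entry route (4a or 4b), as a supportive analysis. This is an addition, not part of the correction.

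**Cost.** Wording only, with no new scans or subjects. The price is a smaller analysis set for the imaging outcome and a less favourable stated figure.
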